7.2.7. Additional Analysis of Adverse Events

7.2.7.1. Renal Events

Preferred terms for renal events are from the acute renal failure Standardised MedDRA Query (SMQ). The selected PT listing was provided by Gilead GLPS and reviewed by Gilead medical monitors (see details in [Appendix 3](#)).

Treatment-emergent renal AEs will be summarized by PT only, in descending order of total frequency. In addition, treatment-emergent renal AEs will be listed.

7.2.7.2. Hepatic Events

Liver function test increased events include ALT increased, AST increased, hepatic enzyme increased, hypertransaminasaemia, liver function test increased, and transaminaseses increased. Preferred terms for hepatic events are from the search term list ‘Acute and non-infectious liver events.’ The selected PT listing was provided by Gilead GLPS and reviewed by Gilead medical monitors (see details in [Appendix 4](#)).

Treatment-emergent liver function test increased AEs and hepatic events will be summarized by PT only, in descending order of total frequency. An overall summary of treatment-emergent hepatic AEs will be provided. In addition, treatment-emergent hepatic AEs will be listed.

7.3. Laboratory Evaluations

Laboratory data collected during the study will be analyzed and summarized using both quantitative and qualitative methods. Summaries of laboratory data will be provided for the Expanded RDV-Treated Analysis Set and will include data collected up to the last dose of study drug plus 30 days. The analysis will be based on values reported in conventional units. When values are below the LOQ, they will be listed as such, and the closest imputed value will be used for the purpose of calculating summary statistics as specified in [Section 3.7](#).

A by-subject listing for laboratory test results will be provided by subject ID number and visit in chronological order for hematology, serum chemistry, and PCR separately. Values falling outside of the reference range and/or having a severity grade of 1 or higher on the DAIDS Grading Scale will be flagged in the data listings, as appropriate.

7.3.1. Summaries of Numeric Laboratory Results

Descriptive statistics will be provided by group for each laboratory test as follows:

- Baseline values
- Values at each postbaseline analysis window
- Change from baseline at each postbaseline analysis window

A baseline laboratory value will be defined as the last nonmissing value obtained on or prior to the date (and time, if applicable) of first dose of study drug. Change from baseline to a postbaseline visit will be defined as the postbaseline value minus the baseline value. The mean, median, Q1, Q3, minimum, and maximum values will be displayed to the number of digits indicated in [Appendix 2](#).

In the case of multiple values in an analysis window, data will be selected for analysis as described in [Section 3.8.3](#).

7.3.2. Graded Laboratory Values

The DAIDS Table for Grading the Severity of Adult and Pediatric Adverse Event, Version 2.1 (July 2017) will be used for assigning toxicity grades (0 to 4) to laboratory results for analysis. Grade 0 includes all values that do not meet the criteria for an abnormality of at least Grade 1. For laboratory tests with criteria for both increased and decreased levels, analyses for each direction (ie, increased, decreased) will be presented separately.

7.3.2.1. Treatment-Emergent Laboratory Abnormalities

Treatment-emergent laboratory abnormalities are defined as values that increase at least 1 toxicity grade from baseline at any postbaseline time point, up to and including the date of last dose of study drug plus 30 days. If the relevant baseline laboratory value is missing, any abnormality of at least Grade 1 observed within the time frame specified above will be considered treatment emergent.

7.3.2.2. Summaries of Laboratory Abnormalities

The following summaries (number and percentage of participants) for treatment-emergent laboratory abnormalities will be provided by laboratory test and group; participants will be categorized according to the most severe postbaseline abnormality grade for a given laboratory test:

- Treatment-emergent laboratory abnormalities
- Treatment-emergent Grade 3 and 4 laboratory abnormalities

For all summaries of laboratory abnormalities, the denominator is the number of participants with nonmissing postbaseline values up to 30 days after last dosing date.

A by-subject listing of laboratory abnormalities and Grade 3 or 4 laboratory abnormalities will be provided by subject ID number and visit in chronological order.

7.4. Body Weight, and Vital Signs

Descriptive statistics will be provided by group for body weight, and vital signs (including heart rate, respiratory rate, blood pressure) as follows:

- Baseline value
- Values at each postbaseline visit
- Change from baseline at each postbaseline visit

A baseline value will be defined as the last available value collected on or prior to the date/time of first dose of study drug. Change from baseline to a postbaseline visit will be defined as the postbaseline value minus the baseline value.

In the case of multiple values on one Study Day, data will be selected for analysis as described in Section 3.8.3.

Temperature will not be summarized due to different methods of measuring temperature. SpO₂ and PaO₂ will not be summarized due to multiple measures through varying oxygen supplementation methods.

A by-subject listing of body weight, BMI, and vital signs (including heart rate, respiratory rate, temperature, and blood pressure) will be provided by subject ID number and visit in chronological order. Similarly, a by-subject listing of oxygen saturation (including oxygen delivery mode, oxygen concentration, oxygen flow, SpO₂, and PaO₂) will be provided.

7.5. Prior and Concomitant Medications

Concomitant use of traditional herbal treatments including herb sho-saiko-to (or Xiao-Shai-Hu-Tang) or investigational agents with putative antiviral activity for COVID-19 including approved HIV protease inhibitors like lopinavir/ritonavir, chloroquine, interferon, etc is prohibited in participants receiving RDV.

Concomitant use of investigational agents such as approved HIV protease inhibitors like lopinavir/ritonavir, chloroquine, interferon, etc while receiving RDV is prohibited due to lack of evidence on additive or synergistic effects and potential for an increased risk of transaminase elevations.

Concomitant medications are defined as medications taken while a participant took study drug. Use of concomitant medications will be summarized by preferred name using the number and percentage of participants for each group. A participant reporting the same medication more than once will be counted only once when calculating the number and percentage of participants who received that medication. The summary will be ordered by preferred name in descending overall frequency. For drugs with the same frequency, sorting will be done alphabetically.

For the purposes of analysis, any medications with a start date prior to or on the first dosing date of study drug and continued to be taken after the first dosing date, or started after the first dosing date but prior to or on the last dosing date of study drug will be considered concomitant medications. Medications started and stopped on the same day as the first dosing date or the last dosing date of study drug will also be considered concomitant. Medications with a stop date prior to the date of first dosing date of study drug or a start date after the last dosing date of study drug will be excluded from the concomitant medication summary. If a partial stop date is entered, any medication with the month and year (if day is missing) or year (if day and month are missing) prior to the date of first study drug administration will be excluded from the concomitant medication summary. If a partial start date is entered, any medication with the month and year (if day is missing) or year (if day and month are missing) after the study drug stop date will be excluded from the concomitant medication summary. Medications with year missing from start date (but with day and/or month) will be considered concomitant unless the stop date is prior to the first dosing date. Medications with completely missing start and stop dates will be included in the concomitant medication summary, unless otherwise specified.

Summaries of concomitant medications will be provided for the Expanded RDV-Treated Analysis Set. Participants with any prior and/or concomitant medications will be listed.

7.6. Other Safety Measures

A data listing will be provided for participants experiencing pregnancy during the study.

7.7. Subject Subgroup for Safety Endpoints

Incidence of all treatment-emergent AEs will be repeated within each subgroup defined in Section 3.4.2 using the Expanded RDV-Treated Analysis Set.

7.8. Changes from Protocol-Specified Safety Analyses

There are no changes from the protocol-specified safety analysis.

CCI

[Redacted]

CCI

CCI

10. SOFTWARE

SAS® Version 9.4 (SAS Institute Inc., Cary, NC.) is to be used for all programming of tables, listings, and figures.

PASS Version 14 (NCSS, LLC, Kaysville, Utah) was used for planned sample size and power calculation.

11. SAP REVISION

Revision Date	Section	Summary of Revision	Reason for Revision

12. APPENDICES

- Appendix 1. Study Procedures Table
- Appendix 2. Programming Specifications
- Appendix 3. Renal Events
- Appendix 4. Hepatic Events

Appendix 1. Study Procedures Table

	Screening	Baseline / Day 1 ^b	Day 2	Day 3	Day 4	Day 5	Days 6 and 7	Day 8	Day 9	Day 10	Days 11, 12 and 13	Day 14	Day 28 ^c Follow-up (±5 days)
Written Informed Consent	X												
Medical History	X												
Physical Examination	X	X	X	X	X	X	X	X	X	X	X	X	X
Height	X												
Vital Signs ^a	X	X	X	X	X	X	X	X	X	X	X	X	X
Study Laboratory Testing	X	X		X		X		X		X		X	
Respiratory Status	X	X	X	X	X	X	X	X	X	X	X	X	X
Ordinal Scale		X	X	X	X	X	X	X	X	X	X	X	X
Pregnancy Test	X												

CCI

RDV Dosing for Group 1		X	X	X	X	X							
RDV Dosing for Group 2		X	X	X	X	X	X	X	X	X			
Adverse Events	X	X	X	X	X	X	X	X	X	X	X	X	X
Concomitant Medications	X	X	X	X	X	X	X	X	X	X	X	X	X

- a Includes heart rate, respiratory rate, temperature, blood pressure, SpO₂ at rest, and body weight. Body weight collected on screening and Day 1 and otherwise if available.
- b Assessments need not be repeated if performed the same calendar day as screening procedures.; data collection other than adverse events should stop Day 14 or discharge whichever is earlier.
- c Day 28 evaluations completed if the visit is conducted in person. Only AEs, ordinal scale, and concomitant medication review completed if visit conducted by phone.

Appendix 2. Programming Specifications

- 1) If the age from the Day 1 eCRF is not available, age will be calculated as follows:

Only year is provided for the date of birth (DOB). Use July 1 for the month and day.

- a) AGE (years) is calculated from the number of days between the DOB and Study Day 1,
- b) Use the SAS INTCK function to determine the number of “1st-of-month days” (eg, January 1st, February 1st, March 1st) between DOB and Day 1 (inclusive),
- c) Divide the result in (b) by 12,

AGE = the integer of the result in (c),

Age for laboratory test reference range will be based on the age at the sample collection date.

- 2) All screened participants refer to all participants who are screened (ie, with non-missing screening date) and have a screening number. For summaries the same participant is counted only once.
- 3) Screen failure participants are the participants who were screened and answered “No” for any inclusion criteria or “Yes” for any exclusion criteria regardless of which version of protocol the participant was consented to.
- 4) Participants in the enrolled analysis set are defined as participants enrolled into the study. IXRSRAND is the source to determine whether the participant is enrolled (ie, participant with non-missing ENRD TN in the IXRSRAND dataset), and confirmed by the eCRF ENROLL dataset (ie, ENROLLYN = “Yes” in ENROLL dataset).
- 5) Treatment (ie, TRT01P in ADSL) is derived from IXRSRAND, while actual treatment received (ie, TRT01A in ADSL) is based on the baseline ordinal scale reported at the pre-dose timepoint. If the participant was never dosed, actual treatment received will be assigned as “Never Dosed.”
- 6) In the disposition table, the reasons for premature discontinuation are displayed in the order as they appear on the eCRF.
- 7) Body mass index (BMI)

BMI will be calculated only at baseline as follows:

$$\text{BMI} = (\text{weight [kg]}) / (\text{height [meters]}^2)$$

Baseline height and weight will be used for this calculation if available.

8) Definition of worst values for laboratory, SpO₂ and PaO₂ results.

Test	Result
ALT	Highest result
AST	Highest result
Creatinine	Highest result
Glucose	Highest result if any >ULN and none <LLN Lowest result if any <LLN and none >ULN Otherwise use the average
Total bilirubin	Highest result
Creatinine Clearance	Lowest result
Hemoglobin	Lowest result
Hematocrit	Lowest result
Platelet count	Lowest result
WBC	Lowest result
SpO ₂	Lowest result
PaO ₂	Lowest result

If there are 2 values with the same “worst” numerical result on the same day, the later value is chosen.

9) For demographics tables, “Not Permitted”, “Unknown”, or missing categories will be excluded from percentage with the exception of Race Category where “Not Permitted” is included in “Other.”

10) Confidence Interval for single percentage

The 95% CI for percentage estimate for each group is calculated based on the Clopper-Pearson exact method.

```
proc freq;
  by trt;
  tables event/ binomial;
  exact binomial;
run;
```

11) Competing risk analysis

EVENT = 1 if the participant had the event; EVENT = 2 if the participant died prior to having the event, and EVENT = 0 if the participant did not have the event and did not die.

SAS code to obtain a cumulative incidence function plot and dataset for further processing for time to first event table:

```
proc lifetest outcif outcif plots cif;
  strata trt;
  time days*event(0) / failcode 1; *Note: this produces data for the event of interest only;
run;
```

SAS code to obtain support tables:

```
proc univariate;
  by trt event;
  var days;
  output pctlpre P_min min max max pctlpts 10, 25, 50, 75, 90;
run;
```

12) TEAE

Events with Missing Onset Day and/or Month

An event is considered treatment emergent if any of the following 3 criteria are met:

- i. The month and year (or year) of onset date is the same as or after the month and year (or year) of the first dose of study drug, and
- ii. The month and year (or year) of the onset date is the same as or before the month and year (or year) of the 30th day after the date of the last dose of study drug, and
- iii. End date is as follows:

The (complete) end date is on or after the first dose date, or

The month and year (or year) of end date is the same or after the month and year (or year) of the first dose of study drug, or

End date is completely missing

Events with Completely Missing Onset Date

An AE with a completely missing onset date is defined as TEAE if end date meets any of the 3 criteria specified above.

13) The precision in reporting numerical values should be as follows:

Raw measurements will be reported the same as the data captured electronically or on the eCRF for all but hematology and chemistry values.

The precision for reporting numerical values for hematology and chemistry is as follows:

Laboratory category	Laboratory parameter	Number of digits after the decimal place for mean, median, minimum, Q1, Q3, maximum
Hematology	Hemoglobin (g/dL)	1
Hematology	Hematocrit (%)	1
Hematology	Platelet count (x10 ⁹ /L)	0
Hematology	WBC (x10 ⁹ /L)	2
Chemistry	ALT (U/L)	0
Chemistry	AST (U/L)	0
Chemistry	Total bilirubin (mg/dL)	2
Chemistry	Glucose (mg/dL)	0
Chemistry	Serum creatinine (mg/dL)	2
Chemistry	Creatinine Clearance by Cockcroft Gault (mL/min)	1

Standard deviation and standard error will be reported to one more significant decimal place than the raw measurement.

Mean, median, minimum, Q1, Q3, and maximum will be reported to the same number of decimal places of the raw measurements.

Exceptions may be considered; for example, if more than 4 significant digits are provided for the measurement.

- 14) Last dose date is not expected to be missing. However, if last dose date is missing, it will be imputed using the maximum of non-missing, non-zero dose, study drug start and stop dates.
- 15) Incomplete death dates will be imputed as the maximum of the study drug start dates (lasfdt), study drug end dates (lasldt), clinic visit dates (lvis28dt), laboratory visit dates (llab28dt), including the 28-day follow-up visit date plus 1, ie dthdt
 $\max(\text{lasfdt}, \text{lasldt}, \text{lvis28dt}, \text{llab28dt}) + 1$.
- 16) Ordinal scale and oxygen support status

The oxygen support status is derived from the ordinal scale:

Ordinal Scale		Oxygen Support Status
1	Death	Death
2	Hospitalized, on invasive mechanical ventilation or ECMO	Invasive Mechanical Ventilation
3	Hospitalized, on non invasive ventilation or high flow oxygen devices	High Flow Oxygen
4	Hospitalized, requiring low flow supplemental oxygen	Low Flow Oxygen
5	Hospitalized, not requiring supplemental oxygen requiring ongoing medical care (COVID 19 related or otherwise)	Room Air
6	Hospitalized, not requiring supplemental oxygen no longer requires ongoing medical care (other than per protocol RDV administration)	Room Air
7	Not hospitalized	Discharge

17) Censoring rules

Time to death: participants are censored at the last known date alive (last study day)

Time to ≥ 2 -point improvement, time to ≥ 1 -point improvement, time to recovery; if a participant does not experience the event of interest and does not die, the participant is censored at the last non-missing ordinal scale assessment date.

18) Graded Laboratory Abnormalities Summary

The following labels will be used for laboratory abnormalities and Grade 3 or 4 laboratory abnormalities summary tables and listings:

Battery	Lab Test Label Used in l-labtox Listing	Toxicity Direction	Lab Test Label Used in t-labtox Table
Hematology	Hemoglobin	Decrease	Hemoglobin (Decreased)
	Platelets	Decrease	Platelets (Decreased)
	WBC	Decrease	WBC (Decreased)
Chemistry	ALT	Increase	ALT (Increased)
	AST	Increase	AST (Increased)
	Creatinine	Increase	Creatinine (Increased)
	Creatinine Clearance	Decrease	Creatinine Clearance (Decreased)
	Serum Glucose	Increase	Serum Glucose (Hyperglycemia)
	Serum Glucose	Decrease	Serum Glucose (Hypoglycemia)
	Total Bilirubin	Increase	Total Bilirubin (Hyperbilirubinemia)

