6.5. Day 28 Follow up Assessment (±5 Days)

The following evaluations are to be completed if this visit is conducted in person. For participants who have been discharged from hospital, the final evaluation can be made by phone. Only AE and concomitant medication and ordinal scale (if discharged on or after Day 14) review are to be completed if visit is conducted by phone.

- Physical examination and vital signs (heart rate, temperature, blood pressure)

- Documentation of respiratory status:

Respiratory rate

- Oxygen supplementation: room air, low flow O₂ (L/min and %), high flow O₂ (L/min and %), CPAP/BIPAP (FiO₂ or %), mechanical ventilation (FiO₂ or %), ECMO

Oxygenation: SpO₂ or PaO₂

Radiographic findings (if available)

- Review AEs and document concomitant medications
- Review the Ordinal Scale (Section 6.9). If subject was not discharged by Day 14, any change in category and the date of any change in category from Day 14 to discharge (or Day 28) should be recorded

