6.2. Efficacy Endpoints of Interest

Efficacy endpoints of interest include endpoints based on clinical status assessed by a 7-point ordinal scale. The endpoint will be derived by combining the available death, hospital discharge alive and ordinal scale assessment reported by the site, where death supersedes discharge alive and discharge alive supersedes the ordinal scale score reported by the site.

Sites were instructed to report the worst ordinal scale category for each day. Therefore, the ordinal scale result on the day the participant was discharged alive does not necessarily reflect Not hospitalized (7). The definition of clinical status based on the 7-point ordinal scale is defined as follows:

- If a participant dies while hospitalized (as recorded on the Death eCRF and Hospitalization eCRF), the endpoint on the day of death and all subsequent days through Day 28 will be set to Death (1)
- If the participant is discharged alive, the endpoint on the day of discharge alive and all subsequent days through Day 28 will be set to Not hospitalized (7)
- If the participant is discharged alive and dies on the same day or a later day (as recorded on the Death eCRF and Hospitalization eCRF), the endpoint on the day of discharge alive and all subsequent days until the day of death will be set to Not hospitalized (7). On the day of death and all subsequent days through Day 28, the endpoint will be set to Death (1),

Every effort will be made to obtain clinical status data for all participants prior to discharge alive. The last known clinical status will be used for days with missing clinical status (eg, where the reason for Hospital Discharge is not “Discharged Alive” and the participant has not died). All post-baseline days with missing ordinal scale score, from Day 2 to Day 14 and Day 28, will use the previous last known clinical status.

Efficacy endpoints of interest include

- Clinical status on Days 1 to 14, Day 28 and last available assessment
- Change in clinical status on Days 5, 7, 11, 14, 28, and last available assessment
- Time to clinical improvement (days): Clinical improvement is defined as a ≥ 2 -point improvement from baseline clinical status or discharged alive on the 7-point ordinal scale using the definition specified above.

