6.2.1. Analysis of Efficacy Endpoints of Interest

The number and percentage of participants in each clinical status category for each day from Baseline through Day 14 and at Day 28 and using the last available assessment will be summarized by group. These results will be summarized using (1) the clinical status definition in Section 6.2 and (2) with the definition specified in Section 6.2 but excluding days with missing ordinal scale score not due to death or discharge alive. In addition, stacked bar charts by study day (Baseline through Day 14 and at Day 28) will be produced by group using the definition specified in Section 6.2.

The number and percentage of participants in each clinical status category for each day from Baseline through Day 14 and at Day 28 and last available assessment will be summarized within each subgroup defined in Section 3.4.1.

The change from baseline in clinical status category on Days 5, 7, 11, 14, 28 and last available assessment will be summarized by group using descriptive statistics.

Number of days of oxygen support status modes (invasive mechanical ventilation, high flow oxygen, low flow oxygen) will be calculated as the number of days oxygen support was reported on the 7-point ordinal scale eCRF through death, discharge alive, or Day 14 and presented for each group using descriptive statistics.

A shift table of baseline oxygen support status (death, invasive mechanical ventilation, high flow oxygen, low flow oxygen, room air, discharge alive) to Days 5, 7, 11, 14, 28 and the last available status will be provided for each group.

Duration of hospitalization will be calculated only for participants who are discharged alive on or prior to Day 28 and will be summarized for each group using descriptive statistics.

All-cause mortality will be estimated for each group using the Kaplan-Meier product limit method with all available data. Participants who did not die will be censored at the last study day.

Days to clinical improvement and days to recovery will be estimated for each group using a competing risk analysis approach, with death as the competing risk. Participants without recovery will be censored on the day of the last non-missing ordinal scale assessment.

Forest plots by subgroup will be presented for all-cause mortality Kaplan-Meier estimates on Day 28 and cumulative incidence of recovery on Day 28.

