7.2.5.2. Incomplete Dates

If the onset date of the AE is incomplete and the AE stop date is not prior to the first dosing date of study drug, then the month and year (or year alone if month is not recorded) of onset determine whether an AE is treatment emergent. The event is considered treatment emergent if both of the following 2 criteria are met:

- The month and year (or year) of the AE onset is the same as or after the month and year (or year) of the first dosing date of study drug, and
- The month and year (or year) of the AE onset is the same as or before the month and year (or year) of the date corresponding to 30 days after the date of the last dose of study drug

An AE with completely missing onset and stop dates, or with the onset date missing and a stop date marked as ongoing or on or after the first dosing date of study drug, will be considered to be treatment emergent. In addition, an AE with the onset date missing and incomplete stop date with the same or later month and year (or year alone if month is not recorded) as the first dosing date of study drug will be considered treatment emergent.

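### The SAP's rule for incomplete death dates ignores a recorded month and year, so an imputed death can precede the month on record and distort Day 14 status, the mortality curve and sometimes Day 28 mortality

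*SAP*

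**What the plan says.** SAP Appendix 2, item 15 governs death dates: "Incomplete death dates will be imputed as the maximum of the study drug start dates", study drug end dates, clinic visit dates and laboratory visit dates, "including the 28-day follow-up visit date plus 1". The formula is dthdt = max(lasfdt, lasldt, lvis28dt, llab28dt) + 1. It draws no line between a date lacking only the day and one that is wholly missing, and no other section bounds the result.

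Other partial dates are treated differently. For an incomplete adverse event onset (SAP 7.2.5.2), "then the month and year (or year alone if month is not recorded) of onset determine whether an AE is treatment emergent". SAP 7.5 likewise uses the recorded month and year of partial medication dates.

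The death date feeds several outputs:

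- SAP 6.2.1: "All-cause mortality will be estimated for each group using the Kaplan-Meier product limit method with all available data".
- SAP 6.2.1: "Forest plots by subgroup will be presented for all-cause mortality Kaplan-Meier estimates on Day 28".
- SAP 6.2: clinical status is category 1 from the day of death through Day 28.
- SAP 6.2.1 and Appendix 2, item 11: death is the competing risk for improvement and recovery.
- SAP 7.2.6: treatment-emergent deaths run from first dose to last dose plus 30 days.

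On follow-up, SAP Appendix 1, note b states that "data collection other than adverse events should stop Day 14 or discharge whichever is earlier". The remaining scheduled contact is the Day 28 visit, with a window of ±5 days, and Protocol 6.5 allows it by phone for discharged participants.

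**The concern.** The SAP uses the word incomplete in 7.2.5.2 for dates whose month and year, or year alone, are known. Item 15 uses the same word, so read literally it covers partial death dates and discards the part that was recorded. Scheduled data collection can end early, at discharge or Day 14, so the last listed date may lie well before a death that is known to fall in a later month. The programmed date is then one that the record rules out.

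At stake are the daily clinical status summaries (Day 14 in particular), the shape of the mortality curve, death as a competing event and, in some cases, the Day 28 mortality estimates and their subgroup forest plots.

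**Working it through.** The SAP gives no figure for this rule, so there is none to reproduce. The check applies item 15 to worked cases.

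**Inputs.** Imputed date = latest listed date + 1 (SAP Appendix 2, item 15). Study Day = date − first dose date + 1 (SAP 3.8.1). Follow-up window Day 23 to Day 33 (28 ± 5; Protocol 6.5). Deaths after the follow-up visit are reportable to last dose + 30 days (Protocol 7.3.3), which is Day 40 if the last dose is on Day 10. Calendar dates and contact days below are assumptions for illustration.

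**Example.** First dose 10 April; last listed contact 20 April (Day 11); death recorded as May with no day.

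- Item 15: 20 April + 1 = 21 April, Day 12.
- Earliest date the record allows: 1 May, Day 22.
- The imputed date is therefore at least 22 − 12 = 10 days early.
- Day 14 is 23 April, before any possible date of death, yet status from Day 12 onward is set to Death.
- Day 28 is 7 May. The record allows dates on both sides of it, but item 15 always counts the death by Day 28.

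**How early, for a true death on Day 29 to 40 with an incomplete date.** The last column is the share of cases in which the imputed date precedes the recorded month, over first-dose dates from 1 April to 30 June 2020, all combinations weighted equally.

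| Last listed contact | Imputed day | Days early | Imputed before recorded month |
|---|---|---|---|
| Day 8 | 9 | 20 to 31 | 83% |
| Day 14 | 15 | 14 to 25 | 64% |
| Day 23 | 24 | 5 to 16 | 34% |
| Day 27 | 28 | 1 to 12 | 21% |
| Day 28 or later | 29 or later | n/a | Day 28 mortality not inflated |

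In the first four rows the death counts in Day 28 mortality although it came later.

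**Effect of a first-of-month floor.** In the example, the later of 21 April and 1 May is 1 May, Day 22. Day 14 status is no longer Death and the contradiction is gone. The death still counts by Day 28. In the same grid, about 79% of the true Day 29 to 40 deaths remain on or before Day 28 after the floor, because the first of the month often precedes Day 29.

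**Size per case.** Ignoring censoring, one moved death changes an estimate by about 1/n: 1/5600 = 0.018 percentage points, 1/1000 = 0.1, 1/500 = 0.2, 1/100 = 1.0. Only the Part B total (up to about 5600) is in the documents; the other values of n illustrate groups or subgroups.

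**A related gap.** Item 15 does not name discharge or ordinal-scale dates. A participant discharged alive on Day 25 whose last listed date is Day 14 would be imputed dead on Day 15, ten days before discharge. SAP 6.2 provides for death on or after the day of discharge alive, not before it.

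**The case against.** A reader might infer that the rule always errs early and so biases Day 28 mortality upward. The documents do not support that.

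- The maximum includes the Day 28 visit, so a listed contact on Day 28 to 33 gives Day 29 or later. Inflation needs a true death after Day 28, an incomplete date, and no listed contact on or after Day 28.
- A death on the day after last contact is dated exactly, and a death on the day of last contact is dated one day late. The SAP does not say whether a phone contact at which a death is first learned enters lvis28dt. If it does, a death before Day 28 learned on Day 30 would be imputed to Day 31, which is late.
- An early date for a death that truly fell by Day 28 leaves the Day 28 count unchanged.
- In the example, 24 of the 31 May dates lie after Day 28, but reading that as a probability assumes all are equally likely. With a last dose on 19 April (Day 10), the reporting window in Protocol 7.3.3 ends on 19 May; within 1 to 19 May, 12 of 19 dates lie after Day 28. All 19 are also correctly treatment-emergent, so that output is affected only for 20 to 31 May.

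Frequency is a further objection. Deaths are serious adverse events sent within 24 hours (Protocol 7.3.3.1), reconciled with the safety database (SAP 7.2.4) and queried before the final analysis (SAP 2.2). Nothing shows how many death dates stay incomplete, or that post-discharge deaths are the usual ones.

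All of this stands and limits the size of the point. It does not remove the defect: applied as written, item 15 can give a date that the record excludes.

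**Conclusion.** The point holds as a minor but real flaw in the programming rule. Item 15 can place a death before its recorded month, which wrongly sets Day 14 status to Death when the last listed date is early and drops the mortality curve too soon. Under the conditions named above it also adds the death to Day 28 mortality. It does not establish a general upward bias.

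The size is about 1/n per case: negligible over the whole of Part B, visible only in a small subgroup (1 point at n = 100). The number of cases is unknown and probably small. Part B is descriptive with no formal testing (SAP 3.3), so no inferential conclusion depends on it. The finding rests on reading incomplete as including dates with a known month, which is how SAP 7.2.5.2 uses the word.

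**What to change.** Amend item 15 as follows.

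1. If month and year of death are known, impute the later of last known alive date + 1 and the first day of the recorded month, and never later than the last day of that month. The cap matters too: last contact on 30 April with death recorded as April would otherwise give 1 May.
2. Add discharge-alive and ordinal-scale dates to the dates that define last known alive.
3. If only the year is known, apply the same bounds by year.
4. Use last known alive + 1 alone only when the death date is completely missing.
5. Flag every imputed death date in the dataset and listings.
6. If any such death could fall on either side of Day 28, also report Day 28 mortality with the earliest and the latest possible dates. The first-of-month floor does not settle this by itself.

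The cost is a few lines of programming and at most one small sensitivity table. No new data are needed.
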